6.1.3. Multiple Comparisons

No adjustments will be made for multiple comparisons for any endpoint.

6.1.4. Handling of Dropouts or Missing Data

Subjects who discontinue or are unblinded before Visit 8 may be replaced. Subjects who withdraw or are withdrawn during screening will be replaced. Subjects who have received at least 1 dose but are withdrawn or withdraw from the study will be encouraged to complete the end of study procedures within 4-6 weeks of their last visit.

Missing data will not be imputed.

6.1.5. Analysis Visit Windows

Visits will be analyzed as scheduled. Unscheduled and/or repeated measurements will only be included if a scheduled measurement is not available and the unscheduled/repeated measurement falls within the analysis visit windows as described below. The windows follow the Schedule of Events in Table 1. Unscheduled/repeated measurements will be listed.

Visit	Target Start Day	Lower Limit	Upper Limit
1		-35	-8
2		-7	-1
3	1	1	1
4	2	2	2
5	3	3	3
6	4	4	4
7	5	5	5
8	6	6	9
9	28	21	35
10	56	49	63
11	85	78	92
12	86	79	93
13	87	80	94
14	88	81	95
15	89	82	96
16	90	83	100
17	112	105	119
18	140	133	147
19	168	161	175

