5.3. During the Infusion (Safety Monitoring and Vital Signs)

During the infusion, the blinded Outcomes Assessor’s primary role is to observe the subject for AEs (refer to **Section 6: Monitoring for Adverse Reactions**) and to monitor vital signs (the unblinded Infusion Nurse is responsible for the administration of all infusions). If the subject is not tolerating an infusion well, the blinded Outcomes Assessor will instruct the unblinded Infusion Nurse to stop the infusion and will inform the PI or physician designee that the infusion has been stopped. **This should be done with care taken to not unblind the Outcomes Assessor, the PI, or his/her designee.** For example, if the subject is not tolerating the infusion well and the Blinded Outcomes Assessor asks the Unblinded Infusion Nurse to stop

the infusion, if the subject is receiving placebo, the Unblinded Infusion Nurse must be careful not to unintentionally convey this (e.g. acting surprised that the subject is not tolerating placebo).

The blinded Outcomes Assessor should follow the guidelines below for ALL INFUSIONS:

- a. Monitor and record baseline vital signs not more than one hour prior to infusion start.
- b. Once the infusion is started, record vital signs (seated BP, heart rate (HR), respiration rate (RR), temperature) every 15 minutes (\pm 5 minutes) for the first hour and then every 30 minutes (\pm 5 minutes) thereafter for as long as the infusion continues (up to [REDACTED]). Vital signs can also be recorded ad hoc if the subject is experiencing symptoms that indicate a change in vital signs.

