6. MONITORING FOR ADVERSE REACTIONS

Throughout the infusion, the blinded Outcomes Assessor or designee should continuously assess the subject for signs of AEs.

In the event of an AE, the PI or designee physician should be notified, and the event should be recorded for later transcription into the CRF. The PI should assess immediately whether an AE is an AE of special interest and/or an SAE and report it accordingly, as per the protocol.

Table 3. Recommended AE Actions for PI or Physician Designee

Mild Events	

 • Body temperature >38.0°C (>100.4°F) but <39.0°C (<102.2° F) • Chills • Dizziness • Fatigue • Flushing • Mild-to-moderate itching • Redness of skin or rash • Urticaria (hives) in the absence of any other sign of symptom • Nausea / Vomiting 	
Stop the infusion, recheck vital signs, and notify the PI or physician designee. After assessment by a physician and consideration of treatment of fever with acetaminophen (if applicable), the unblinded Infusion Nurse may restart the infusion rate at half the rate at the onset of the infusion event and maintain the reduced rate for at least 30 minutes. If this rate is tolerated, the unblinded Infusion Nurse may increase the rate as tolerated by 30 mL per hour (0.5 mL/min) every 30 minutes (± 5 minutes) as tolerated.

Moderate to Severe Events	

 • Bronchospasm (wheezing, coughing) • Hoarseness or other signs of laryngeal edema • Throat or mouth pain or irritation • Chest pain/back pain • Shortness of breath • Fever ≥39 °C (102.2° F) • Rigors • Hemoglobinuria • Oliguria • Sustained hypertension (systolic BP (SBP) >170 and/or diastolic BP (DBP) >100 not present before the first infusion) • Sustained hypotension (SBP <90 and/or DBP <50 not present before the first infusion) • Tachycardia (HR>100 bpm) • Signs / symptoms of volume overload 	
Stop the infusion, recheck vital signs, and notify the PI or physician designee. The PI or physician designee should administer appropriate supportive treatment, as necessary. The infusion should not be restarted, and the subject should not be dosed further. Notify the Medical Monitor(s) as soon as possible (preferably by end of business day).

Life-Threatening Events	

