9.2. Laboratory Evaluations

The screening safety lab panel includes: all comprehensive labs (hematology, chemistry, coagulation, urinalysis, urine chemistry, ionized calcium), immunochemistry (HIV, hepatitis B, hepatitis C, thyroid-stimulating hormone (TSH), brain natriuretic peptide (BNP)), cobalamin (vitamin B12), pyridoxine (vitamin B6), thiamine (vitamin B1), direct antiglobulin test, IgA, haptoglobin, and C1 inhibitor. The urine drug screen includes cannabinoids, benzodiazepine, barbiturates, opiates, cocaine, amphetamines, methadone, phencyclidine, and propoxyphene.

Pre-infusion safety labs will be performed onsite and should be collected and results interpreted prior to the following day's infusion start. The following should be measured at Visit 3, Visit 4, Visit 6, Visit 11, Visit 12, and Visit 14: sodium (Na), potassium (K), ionized calcium, urea nitrogen (BUN)/urea, creatinine (Crea), hematocrit, hemoglobin, platelets. These results are only available at each site and will therefore not be summarized.

The exit safety lab panel includes all comprehensive labs, immunochemistry, direct antiglobulin test, and ionized calcium.

Comprehensive labs will be performed at screening/Visit 1, Visit 6, Visit 8, Visit 9, Visit 14, Visit 16, Visit 17, and upon exit/Visit 19.

Laboratory test results, excluding the site's pre-infusion safety labs mentioned above, will be summarized descriptively by treatment and visit as both observed values and change from baseline values for each parameter. Categorical urinalysis results will be summarized using frequencies by treatment group and visit.

Shifts from baseline for clinical laboratory values below, within, or above the normal range will be provided for hematology, chemistry, coagulation, and quantitative urinalysis results by visit and treatment. See Section 6.1.1 for the definition of baseline.

Subjects with significant laboratory abnormalities will be identified in data listings. If any laboratory tests are collected at an unscheduled visit post-baseline, the results will be included in listings.

Pregnancy test results from Screening (Visit 1), Visit 3, and Visit 11 will be listed.

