9.3. Vital Signs

Descriptive summaries of actual values and changes from baseline will be calculated for seated systolic blood pressure, standing systolic blood pressure, and supine systolic blood pressure, seated diastolic blood pressure, standing diastolic blood pressure, and supine diastolic blood pressure, heart rate, respiration rate, and body temperature. These summaries will be presented by visit and treatment group. Vital signs are collected at all study visits. During the infusion periods (Visit 3-Visit 7 and Visit 11- Visit 15), orthostatic vital signs (supine systolic and supine diastolic blood pressure compared to standing systolic and standing diastolic blood pressure) should be measured prior to infusion start and at approximately [REDACTED] after infusion start. Seated systolic and seated diastolic blood pressure is measured at multiple timepoints during and after each infusion. Abnormal vital sign values will be flagged in the listings. Abnormal vital sign values are as follows:

- Seated systolic blood pressure value < 90 mmHg
- Seated systolic blood pressure value > 180 mmHg
- Seated diastolic blood pressure value < 50 mmHg
- Seated diastolic blood pressure value > 110 mmHg
- Incidence of orthostatic hypotension (a decrease in systolic blood pressure of > 20 mm Hg and/or a decrease in diastolic blood pressure of > 10 mm Hg between supine and standing)
- Heart rate > 100 beats per minute
- Temperature > 37.5°C
- Temperature < 36.5°C
- Respiration rate > 20 breaths per minute
- Respiration rate < 12 breaths per minute

The vital sign measurements that meet the criteria for blood pressures of special interest (listed below) will also be identified from the vital signs source data and summarized separately by study visit, timepoint, and treatment.

- Seated systolic blood pressure >180 mmHg
- Seated systolic blood pressure > 200 mmHg
- Seated systolic blood pressure < 90 mmHg
- Seated diastolic blood pressure > 110 mmHg
- Seated diastolic blood pressure > 120 mmHg
- Seated diastolic blood pressure < 50 mmHg
- A change of $\geq 30\%$ from baseline in seated systolic and/or seated diastolic blood pressure

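### SAP 6.1.5 keeps symptom-driven vital signs and between-visit labs out of the by-visit summaries and lab shift tables, and leaves their place in the table of blood pressures of special interest unsettled

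*SAP*

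**What the plan says.** SAP 6.1.5 sets one rule for all data: "Unscheduled and/or repeated measurements will only be included if a scheduled measurement is not available", and then only if the reading lies inside an analysis visit window. Everything else goes to listings: "Unscheduled/repeated measurements will be listed".

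The infusion manual in Protocol Appendix 11 fixes the spacing of vital signs during an infusion at 15 minutes "for the first hour and then every 30 minutes". It then adds, in section 5.3: "Vital signs can also be recorded ad hoc if the subject is experiencing symptoms that indicate a change in vital signs". Table 3 in its section 6 tells staff what to do for both mild and moderate-to-severe infusion events: "Stop the infusion, recheck vital signs, and notify the PI or physician designee".

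SAP 9.3 flags abnormal vital signs in listings. BPSIs are to be "identified from the vital signs source data and summarized separately by study visit, timepoint, and treatment". The shell of Table 14.3.6.1.2 shows baseline and nominal times such as 15 and 30 minutes into the Visit 3 infusion.

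For laboratory data, SAP 9.2 says: "If any laboratory tests are collected at an unscheduled visit post-baseline, the results will be included in listings". Shift tables are by visit, significant abnormalities are identified in listings, and the planned table section for abnormal laboratory values (14.3.4, in SAP 13.3) is marked not applicable.

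**The concern.** Safety and tolerability are the primary objective, and Protocol 2.3.1 names hypotension among the product's important identified risks. A reading taken because a subject feels unwell is more likely than a clock-driven one to show an extreme value. If such readings are only listed, the report shows them subject by subject but does not count them by arm.

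The gap matters most for blood pressures that the investigator does not call adverse events. Protocol 8.4.3 says that pressures meeting its limits but not considered adverse events will be analysed separately as BPSIs. SAP 10 leaves to the investigator whether a pressure is an adverse event of special interest (AESI), and brings in the BPSI summaries for that reason. The BPSI table is thus the one by-arm display that does not depend on the investigator's judgement, so which readings feed it should be beyond doubt.

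**Working it through.** The plan states no figure on this point, so there is none to reproduce. The check follows each kind of reading to its display, then asks how far the fallback in 6.1.5 helps.

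**1. Where each reading goes when the scheduled value exists**

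| Reading | By-visit summary | Other by-arm display | Listing |
|---|---|---|---|
| Ad hoc or recheck vital sign, judged an adverse event | No (6.1.5) | Yes, as an event: TEAE table, AESI table if it meets those criteria, blood-pressure-term table (SAP 9.1, 9.1.3) | Yes |
| Ad hoc or recheck blood pressure, not judged an adverse event | No (6.1.5) | BPSI table only, and unresolved there | Yes |
| Unscheduled lab between visits, clinically significant | No (6.1.5, 9.2) | Yes, as an event (Protocol 7.2.1) | Yes |
| Unscheduled lab between visits, not clinically significant | No (6.1.5, 9.2) | None; shift tables are by visit | Yes |
| Repeat of an abnormal scheduled lab | Repeat: no. Abnormal scheduled value: yes | The scheduled value stays in the shift table | Yes |

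**2. The BPSI table**

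- For inclusion: SAP 9.3 draws on the vital signs source data and excludes nothing.
- Against: 6.1.5 is a general rule, and the shell shows only nominal timepoints, with no ad hoc or any-time row.
- Either way, rows by timepoint do not give the number of subjects per arm with at least one qualifying reading.

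Two programmers could follow the SAP faithfully and produce different tables.

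**3. Reach of the fallback**

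The windows in SAP 6.1.5 cover Days 1–9, 21–35, 49–63, 78–100, 105–119, 133–147 and 161–175:

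9 + 15 + 15 + 23 + 15 + 15 + 15 = 107 days.

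The uncovered days are 10–20, 36–48, 64–77, 101–104, 120–132 and 148–160:

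11 + 13 + 14 + 4 + 13 + 13 = 68 days, and 68/175 = 39%.

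An unscheduled value on those days cannot enter even as a substitute. Around the second course the windows overlap: Day 85 lies in all six windows for Visits 11 to 16 (78–92, 79–93, 80–94, 81–95, 82–96, 83–100), so a substitute has no unique visit. The SAP also does not say whether a scheduled measurement is unavailable per visit or per timepoint.

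**4. Illustration: can scheduled readings stand in for ad hoc ones?**

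For an episode of D minutes with random onset and readings every s minutes, the chance that a scheduled reading falls inside it is min(1, D/s). The spacing comes from Appendix 11; the durations are assumed.

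| Assumed D (min) | s = 15 | s = 30 |
|---|---|---|
| 5 | 5/15 = 33% | 5/30 = 17% |
| 10 | 10/15 = 67% | 10/30 = 33% |
| 15 | 100% | 15/30 = 50% |
| 20 | 100% | 20/30 = 67% |
| 30 | 100% | 100% |

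Short episodes can exist only as ad hoc readings; longer ones are caught by the schedule.

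**The case against.** The strongest reply is that the main safety displays are adverse event tables, and these do not depend on 6.1.5. A symptomatic fall in pressure can be recorded as an adverse event. The AESI criteria include a clinically significant systolic pressure below 90 mmHg at a single timepoint, and SAP 9.1.3 adds a by-arm table of blood-pressure terms split by infusion period. The recheck in Table 3 follows an event that has already happened. Clinically significant labs are recorded as adverse events. All of this stands. A reader might infer that these readings are missing from every by-arm safety display, and the documents do not support that. The reply does not cover pressures that are not called adverse events.

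Second, the windows in 6.1.5 are in days and may not be meant for readings minutes apart within an attended infusion visit, and the BPSI shell is only a sample. That is fair: exclusion from the BPSI table is unresolved, not stated. When an infusion is stopped and not restarted, a recheck might even qualify as a substitute for a later timepoint that never occurred.

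Third, a reader might infer that repeating an abnormal scheduled lab loses the worst value. Under the rule, the abnormal scheduled value stays in the shift table and only the repeat drops out. The loss concerns unscheduled labs between visits, and the documents do not say how often these occur.

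Fourth, scheduled-only summaries keep ascertainment equal across arms, whereas symptom-triggered readings give symptomatic subjects more chances to cross a threshold. This stands, and is why both figures are needed. The readings are also not hidden: listings are sorted by treatment, and the blood pressure listing carries abnormal and BPSI flags.

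**Conclusion.** The point holds in limited form. Under SAP 6.1.5 as written, symptom-driven vital signs and between-visit labs are left out of the by-visit vital-sign and laboratory summaries and the lab shift tables whenever the scheduled value exists. No planned table recovers them as an any-time or worst value. For the BPSI table the SAP points both ways. Confidence is high on the by-visit summaries and shift tables, and moderate on the BPSI table.

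The documents do not allow the number of affected readings to be estimated. Two further inferences are tempting and go too far. One is that the tables are biased towards no difference: that follows only if GRF6021 causes more symptoms than placebo, which is not known, and adding symptom-driven readings can itself inflate a difference. The other is that most short falls in pressure would be missing. The capture chances above rest on assumed episode lengths and random onset, they reach 100% for longer episodes, and the manual permits ad hoc readings without requiring one for each episode.

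**What to change.** - In SAP 6.1.5, confine the restriction to by-visit summaries. Say whether unavailability is judged per visit or per timepoint, and give a rule for assigning a value when the windows for Visits 11 to 16 overlap.
- In SAP 9.3, state that BPSI counts use all post-dose readings, scheduled or not.
- In Table 14.3.6.1.2, add per-subject rows by arm for any qualifying post-dose reading, for each infusion course and overall.
- In the lab shift tables (14.3.5.1.2, 14.3.5.2.2, 14.3.5.3.2 and 14.3.5.4.2), add a row for the worst post-baseline value, scheduled or unscheduled.
- Show the scheduled-only figure beside each new row, because symptomatic subjects contribute more readings.

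The cost is some SAP wording and a few derived rows. No new data are collected.

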7.3 STUDY SCHEDULE

To ensure follow-up visits occur at approximately the same intervals following both treatment periods, visit windows should be calculated as follows:

- Visit windows for Visits 1-10 should be calculated relative to Day 1.
- Visit windows for Visits 11-19 should be calculated relative to Day 85 ± 7 (i.e., first day of dosing for Treatment Period 2).

Study visit procedures are listed in the recommended order in which they should be completed.

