7.3.5 FOLLOW-UP

Visits 8 and 16 (Day 6 + 3 Days and Day 90 + 7 Days):

- Review AEs and concomitant medications.
- Collect the following:
 - Vital signs (including sitting, supine, and standing BP) and subject's weight in kilograms.
 - Blood and urine samples for Comprehensive Labs (fasting samples preferred).
 - Samples for proteomics/epigenetics/biobanking (fasting samples preferred).
- Ensure the subject has had an opportunity to eat a meal or snack prior to commencing cognitive and motor testing and that the subject is in the ON state. PD medications should be taken at the standard intervals for each subject and testing should be scheduled to facilitate the subject being in the ON state.
- It is preferred that cognitive and motor function testing is performed in the following order (breaks are permitted between assessments as needed):

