*It is recommended, but not required, that the echocardiogram and screening MRI be performed after all other screening criteria have been met. The echocardiogram and screening MRI may be performed in any order.

X¹: To be performed prior to infusion start.

X ² : To be performed after infusion.
X ³ : To be performed post-infusion (approximately [REDACTED] after infusion start).
X ⁴ : If shipping of study agent to the study site will be required, subjects should be randomized at least 3 days prior to treatment start to ensure study agent availability.
a: The Screening Visit may be split to allow for sufficient time to complete all procedures. AEs and concomitant medications should be reviewed during split visits, as applicable.
b: The treatment window is 5 days. Visits 8 and/or 16 may occur 1-3 days later.
c: The visit window for Visit 11 is Day 85 ±7 days. Visits 12-15 should follow consecutively.
d: Blood pressure (BP) should be taken after the subject has been lying down for at least 10 minutes (supine). The subject should then stand for 3 minutes, and the BP should be taken again.
e: Includes all comprehensive labs, infectious serology (HIV, HBV, HCV), cobalamin (vitamin B12), pyridoxine (vitamin B6), thiamine (vitamin B1), TSH, direct antiglobulin test, BNP, serum IgA, haptoglobin, and C1 inhibitor (availability of C1 inhibitor lab results not required for evaluation of I/E criteria). Urine drug screen: cannabinoids, benzodiazepine, barbiturates, opiates, cocaine, amphetamines, methadone, phencyclidine, propoxyphene. Urinalysis: UPCR.
f: Includes all comprehensive labs, infectious serology, and direct antiglobulin test.
g: Samples for local pre-infusion labs should be collected and results interpreted PRIOR to the following day's infusion start. The following should be measured: sodium, potassium, ionized calcium, BUN, creatinine, hematocrit, hemoglobin, platelets.
h: Serum pregnancy test required at screening. Serum and/or urine pregnancy test may be used at subsequent timepoints. Results from pregnancy tests conducted at Visits 3 and 11 must be available prior to dosing.

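### SAP 6.1.5 counts the Period 2 windows from Day 1, so a fallback reading taken before or during course 2 can be tabulated as post-course Visit 16

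*SAP*

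**What the plan says.** SAP 6.1.5 works from the nominal visit: "Visits will be analyzed as scheduled". An unscheduled or repeated reading is a substitute, admitted only "if a scheduled measurement is not available and the unscheduled/repeated measurement falls within the analysis visit windows as described below". The table then gives fixed study-day limits: Visit 11, 78 to 92; Visit 12, 79 to 93; Visit 13, 80 to 94; Visit 14, 81 to 95; Visit 15, 82 to 96; Visit 16, 83 to 100. Of their source it says: "The windows follow the Schedule of Events in Table 1". It has no rule for a reading that fits several windows, none that limits a reading to one use, and none that a Visit 16 substitute must follow the last infusion.

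SAP Table 1 (section 3.7) attaches the tolerance to the start of course 2: "The visit window for Visit 11 is Day 85 ±7 days. Visits 12-15 should follow consecutively". It gives Visit 16 as Day 90 with up to 3 days after.

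Protocol 7.3 (V5.0) uses a different anchor: "Visit windows for Visits 11-19 should be calculated relative to Day 85", with a 7-day tolerance, which it explains as the first dosing day of Treatment Period 2. Note c of the protocol's schedule repeats this for Visits 16 to 19. Protocol 7.3.5 gives Visit 16 as Day 90 with up to 7 days after.

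Within Visits 11 to 16 the assessments differ. Vital signs are taken at every visit (SAP 9.3). For laboratory tests, SAP 9.2 says: "Comprehensive labs will be performed at screening/Visit 1, Visit 6, Visit 8, Visit 9, Visit 14, Visit 16, Visit 17", plus the exit visit. ECGs fall at Visits 11 and 15 only (SAP 9.4). D-KEFS, MDS-UPDRS and dCDT fall at Visit 16 only (SAP 8.2).

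**The concern.** Counting from Day 1 works for course 1, because Day 1 is the first infusion. Visits 3 to 7 have single-day windows, Visit 8 has Days 6 to 9, and none overlap. The first infusion of course 2 may fall on any of 15 days, so study day alone no longer shows whether a reading came before, during or after the infusions.

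Visit 16 is meant to show the subject's state just after course 2. A value from before S reflects no course 2 exposure, and a value from within the course reflects only part of it. Either one, tabulated at Visit 16, blurs the before-and-after contrast in the laboratory change and shift tables, the vital signs summaries and the efficacy scales. The overlap adds a second problem: one value could stand at two visits that are meant to describe different moments.

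**Working it through.** **Inputs.** The six windows (SAP 6.1.5); permitted course 2 start S = Day 78 to 92, with infusions on S to S+4 (SAP Table 1); protocol Visit 16 window S+5 to S+12 (Day 90 is 5 days after Day 85, plus 7); visits at which each assessment is scheduled (SAP 8.2 and 9.2 to 9.4).

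**Step 1: reproduce the SAP rows.** For Visits 11 to 15, let k = 0 to 4 be the days after S. The earliest permitted day is 78+k and the latest is 92+k, which gives 78–92, 79–93, 80–94, 81–95 and 82–96. For Visit 16 the earliest is 78+5 = 83 and the latest is 92+5+3 = 100. All six rows match. Each row is the full set of days on which that visit could fall in some subject.

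**Step 2: apply the Visit 16 row to one subject.** The row holds 100−83+1 = 18 days. For a given S:
- pre-course days = S−83 if S is above 83, otherwise 0
- on-course days = 5 if S is 83 or later, otherwise S−78
- post-course days = 100−(S+4) = 96−S

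| S | Pre-course | On-course | Post-course |
|---|---|---|---|
| 78 | 0 | 0 | 18 |
| 79 | 0 | 1 | 17 |
| 84 | 1 | 5 | 12 |
| 85 | 2 (Days 83–84) | 5 (Days 85–89) | 11 |
| 92 | 9 (Days 83–91) | 5 (Days 92–96) | 4 (Days 97–100) |

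Some on-course day qualifies for every start from Day 79 on, and some pre-course day for every start from Day 84 on.

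**Step 3: compare the upper limit with the protocol.** Protocol days lost = (S+12)−100 when positive. S = 89 loses 1, S = 90 loses 2, S = 91 loses 3 and S = 92 loses 4 (Days 101–104). For these starts the rule can accept a pre-course reading and refuse a valid post-course one.

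**Step 4: overlap** (largest lower limit to smallest upper limit).
- Neighbouring rows share 14 days.
- All six rows share Days 83–92, 10 days.
- Laboratory tests, Visits 14 and 16: Days 83–95, 13 days.
- ECG, Visits 11 and 15: Days 82–92, 11 days.
- D-KEFS, MDS-UPDRS and dCDT: Visit 16 only, so no double use; the issue there is a mislabelled reading.

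**Step 5: anchor to S.** Visits 11 to 15 become S, S+1, S+2, S+3 and S+4, and Visit 16 becomes S+5 to S+12. With no grace day, no two windows share a day, and no pre-course or on-course day lies in Visit 16.

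**The case against.** The strongest reply is that nothing in the table is miscalculated. A reader might infer that the tolerance for the course 2 start was carelessly copied onto each dosing day. Step 1 shows otherwise: each row is the exact range that a Day 1 count must cover when the start can move by 7 days either way. The fault is the anchor together with the missing assignment rule. The SAP also names protocol V4.0 as its basis, whereas the anchor compared here is in V5.0. That explains the gap, but SAP version 4.0, dated 17 August 2020, postdates protocol V5.0 of 23 September 2019 and keeps the Day 1 count.

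A reader might also infer that one reading will commonly fill six visits. That needs all six scheduled readings to be missing, and it can apply only to vital signs, weight and supine/standing blood pressure. Vital signs are due before every infusion, so a subject who starts course 2 should already have Visit 11. Laboratory tests and ECGs reach two visits at most.

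A third tempting inference is that the affected subjects are mainly those who stopped after a safety event. The documents give no such figure, and SAP 7.1 anticipates visits missed because of COVID-19.

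For laboratory tests, SAP 9.2 says unscheduled post-baseline results go into listings. It does not say they go only there, so whether 6.1.5 also puts them in tables is unclear. More generally, the SAP does not direct reuse of a reading; it only fails to bar it. These limits stand. They do not remove the main point: a pre-course or on-course reading meets the written condition for Visit 16.

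**Conclusion.** The point holds as a minor defect in a stated rule. For a nominal Day 85 start, 7 of the 18 Visit 16 days (2 + 5) precede or fall within course 2. Across permitted starts this runs from 0 of 18 (Day 78) to 14 of 18 (Day 92). Double use is possible for laboratory tests at Visits 14 and 16 and for ECGs at Visits 11 and 15. Vital signs, weight and supine/standing blood pressure could fill more visits only if several scheduled readings are missing.

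The day counts assume five consecutive infusion days without a grace day. The consequence requires a missing scheduled reading and an unscheduled one inside the window; the documents do not allow the number of such cases to be estimated. The effect of these rows is confined to fallback readings in by-visit efficacy and secondary safety tables. The incidence of TEAEs and SAEs uses no visit window and is unaffected.

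**What to change.** Before unblinding, derive a Period 2 day from S, as Protocol 7.3 requires, and use it for Visits 11 to 19.

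- **Visits 11 to 15:** the day of the corresponding infusion, allowing the grace day. If that infusion was not given, leave the visit missing and map no unscheduled reading to it.
- **Visit 16:** S+5 up to the protocol limit, and after the last infusion. Both conditions are needed. The S+5 floor keeps a reading taken soon after an early stop from becoming Visit 16, and the second condition covers a course extended by the grace day.
- **Visits 17 to 19:** the existing tolerance, counted from S.
- **Assignment:** use each unscheduled or repeated reading for one visit only.
- **No Period 2 infusion:** S does not exist, so state that no fallback applies to Visits 11 to 16 and which anchor serves Visits 17 to 19.

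The cost is one derived variable, the Period 2 rows of the window table and a sentence on assignment. Data collection does not change. One knock-on effect needs checking: SAP section 5 uses the 6.1.5 windows for Visits 18 and 19 to define the Per Protocol Set, so re-anchoring those rows can change membership of that set.
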